### Cognitive Tests

*NIH EXAMINER*: this is a computer based standardized assessment that tests the cognitive/executive domains of planning, set shifting, working memory, inhibition, and fluency. It calculates separate factor scores for each domain as well as a composite executive score.

*Tower of Hanoi*: the objective of this puzzle is to move a stack of differently sized disks from one rod to another while obeying the following rules: only one disk can be moved at a time; a disk can only be moved if it is the uppermost disk on a stack; no disk may be placed on top of a smaller disk. The time and number of moves to complete the puzzle will be recorded.

*Trail making Tests A & B:* The task requires a subject to connect a sequence of 25 consecutive targets on a sheet of paper or computer screen, similar to a connect-the-dots puzzle. There are two parts to the test: in the first, the targets are all numbers (1, 2, 3, etc.) and the test taker needs to connect them in sequential order. In the second part, the subject alternates between numbers and letters (1, A, 2, B, etc.). The goal of the test is for the subject to finish both parts as quickly as possible, with the time taken to complete the test being as the primary outcome.

*Digit Span Test:* memory span is the longest list of items that a person can repeat back in correct order immediately after presentation. The task is known as digit span when numbers are used.

During all cognitive tests, prefrontal cortical activity may be recorded with functional near infrared spectroscopy, which is described below.

### **Functional near infrared spectroscopy (fNIRS)**

fNIRS is a safe non-invasive technology for indirectly assessing cortical activation based on changes in blood flow and oxygenation. Sensors are placed on the forehead, and produce infrared light that is able to pass through the skull and is absorbed or reflected by blood and other tissues in the head. Infrared light is considered safe and there is no sensation association with this procedure. Calculations made from the relative amount of light absorption/reflection provide an estimate of the metabolic activity level of underlying cortical tissue. We will use a commercially available fNIRS monitor (Octamon by Artinis Medical Systems).

### **Sympathetic nervous system activity measured by skin conductance**

During any walking or cognitive task, participants may be asked to wear sensors on their fingers that measure skin conductivity, which is a probe of sympathetic nervous system arousal.

---

### **Rehabilitation Intervention**

Participants will take part in a 6-week, 18-session neurorehabilitation led by qualified and trained study personnel. Participants will be randomized to one of three groups: 1) standard walking neurorehabilitation with sham tDCS ('standard/sham' group), 2) complex walking neurorehabilitation with sham tDCS ('complex/sham' group), or 3) complex walking neurorehabilitation with active anodal tDCS ('complex/active' group). Training logs will be maintained to gauge the content and intensity of training. To control for intensity, participants will maintain a rating of perceived exertion of 4 (moderate to strong) on the Borg Category/Ratio Scale during walking. Exertion will be adjusted by modifying walking speed and/or by modifying the rest time between walking bouts. Training logs will also include information on attendance and adverse events. From these logs we will determine adherence (# of sessions attended), retention (completion of rehabilitation and post-therapy assessment) and number of adverse events.

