**Specific Aim 2: Demonstrate feasibility/safety of tDCS as an adjuvant to rehabilitation.**

Hypothesis 2: The study interventions will not significantly differ for adherence, retention, or adverse events.

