## **6. Research Plan:**

### Study Overview

All study procedures will be conducted at the University of Florida.

Up to thirty older men and women will be enrolled in the intervention component of this study. A larger number will be enrolled for onsite screening, because some will fail the screening tests and not proceed to the study intervention. Volunteers will undergo the following sequence of events:

- *Telephone Screening*: Volunteers will be screened by telephone to determine if they meet basic enrollment criteria including age and general health status.
- *1st Informed Consent and Onsite Screening*: Volunteers who pass the phone screen will be invited to participate in on-site screening. Informed consent for screening will be obtained. Mobility function and cognitive screening will be conducted, including 10m walk speed and tests from the cognitive battery of the NIH Toolbox. Other criteria listed in Table 6 will also be evaluated. Screening will be conducted over two visits lasting approximately 4 hours and 3 hours, respectively. A third visit may sometimes be needed if all assessments cannot be completed in the two visits
- *2nd Informed Consent and Baseline Assessment*: Qualifying volunteers will be invited to participate in the full study. They will attend a baseline assessment session which will include Informed Consent for full study participation and tests of the primary and secondary study outcomes including Figure-8 walk test and NIH EXAMINER battery of executive function. Secondary outcomes will also be evaluated as described in the Research Plan. This visit will last approximately 3 hours.
- *Rehabilitation Intervention*: Enrolled participants will receive 18 sessions of neurorehabilitation, which will be combined with either active or sham tDCS. These sessions will be completed over the course of 6 weeks. Each session will last about 75 minutes from arrival to departure.
- *Post-Intervention Assessment*: At the completion of the neurorehabilitation program, participants will attend a post-therapy assessment session that is identical to the baseline assessment.
- *Three month follow up Assessment*: Three months after completing the neurorehabilitation program, participants will attend a 3-month follow up assessment session that is identical to the baseline and post-treatment assessments.

---

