#### **7. Possible Discomforts and Risks:**

As with all physical activity, there is a risk of falling while we test or train walking ability. Falls can lead to injuries ranging from minor to serious. It is also possible that participants could experience musculoskeletal injury such as an ankle sprain. It is possible that the participant may experience fatigue, soreness, and discomfort due to physical activity associated with this study. These are unlikely to be worse than what he/she would experience due to increased physical activity outside of our study. These are normal responses to exercise and most discomfort would generally disappear within a matter of days. In general, walking exercise is strongly recommended for all adults, including elderly adults with medical conditions.

Transcranial direct current stimulation is considered safe but some people do experience some side effects. The most common side effects are itching and tingling or mild discomfort at the area of stimulation, and headache. Other possible but uncommon side effects include dizziness and nausea. Whenever an electrical stimulation is applied to the body, it could possibly cause a

seizure or abnormal heartbeat, but this has never occurred with the transcranial direct current stimulation parameters used in this study. tDCS will be applied and operated by research personnel listed in myIRB (with all required training in human subjects research) who have been thoroughly trained in the use and safety of tDCS by the investigative team.

fNIRS is considered safe. The infrared light used in assessment is not known to cause any harm to alter the brain in any way. The sensors are secured to the participant's head using adhesive tape, which may cause minor skin irritation in some people, or more substantial irritation in people who are sensitive/allergic to adhesives. We will check with participants about any known sensitivities to adhesives.

There is a risk that participants may find cognitive and functional tests challenging or uncomfortable if they have difficulty succeeding with the tasks. Participants may skip any question that they do not wish to respond do.

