### ***Adverse Event Reporting***

Adverse events (including expected, unexpected, serious and non-serious) will be tracked in a cumulative table. Adverse events will be reported according to the guidelines of the University of Florida Institutional Review. Specifically, adverse events that are serious and unexpected (see definitions below) will be reported to the UF IRB within 5 working days of when study personnel learned about it. Reports of adverse events that are not serious or that are expected (e.g., muscle soreness) will be added to the cumulative adverse event table and reported to the UF IRB annually.

A *serious adverse event* is any adverse event that results in any of the following outcomes:

- death,
- a life-threatening adverse event,
- inpatient hospitalization or prolonging existing hospitalization,
- a persistent or significant disability/incapacity,
- or a congenital anomaly/birth defect.

Important medical events that may not result in death, be life-threatening, or require hospitalization may be considered a serious adverse event when the event may jeopardize the patient or subject and/or may require medical or surgical intervention to prevent one of the outcomes listed in the definition above.

An *unexpected adverse event* is any adverse event that is not consistent with the current investigator brochure, protocol, consent form, or is not part of the normal disease progression. In addition, known adverse events may occur more frequently than expected. If so, then this meets the definition of “unexpected” and must be reported to the IRB.

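### Aim 2's adverse-event outcome is a raw count from the training logs, with no denominator or stated window, although a wider event table is already kept

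*Combined protocol and SAP*

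**What the plan says.** Specific Aim 2 concerns the feasibility and safety of tDCS as an adjuvant, and its hypothesis reads: "The study interventions will not significantly differ for adherence, retention, or adverse events".

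The measures are defined once, in section 6 under Rehabilitation Intervention. The training logs record training content and intensity, and "Training logs will also include information on attendance and adverse events". The protocol then says: "From these logs we will determine adherence (# of sessions attended), retention (completion of rehabilitation and post-therapy assessment) and number of adverse events". The programme they document is the 18-session one: "Participants will take part in a 6-week, 18-session neurorehabilitation led by qualified and trained study personnel". Under Protection Against Risk, the paragraph on safety during neurorehabilitation has the same scope, placing falls and near-falls in those sessions on the therapy log.

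The Data and Safety Monitoring Plan describes a second, wider record under Adverse Event Reporting: "Adverse events (including expected, unexpected, serious and non-serious) will be tracked in a cumulative table". That section uses the table for reporting to the IRB and does not mention Aim 2.

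Section 10, the Statistical Analysis Plan, asks for effect sizes from group means and standard deviations for each hypothesis's primary outcome. It gives no observation window, exposure adjustment or denominator for adverse events.

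**The concern.** Two features of the definition matter.

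**Window.** The protocol expects risk outside training. Section 7 notes: "As with all physical activity, there is a risk of falling while we test or train walking ability". Protection Against Risk also provides for events at screening and assessment visits. The walking tests are repeated after the intervention and again at three months, yet the outcome is drawn from a record of the training programme. The text does not say whether an event at an assessment visit counts, and the follow-up period is outside the logs.

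**Denominator.** The outcome is a number of events, not a rate. Sessions attended is itself an Aim 2 outcome, so the plan allows that it may vary. An arm with fewer attended sessions has fewer occasions on which an event can arise and be logged.

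At stake is the between-arm safety statement carried into the planning of a full-scale trial. It should not depend on how many sessions each arm happened to attend.

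**Working it through.** The plan states no event rate, attendance assumption or power figure for Aim 2, so it has no figure to reproduce. What follows is illustration.

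**Inputs from the documents**
- 18 sessions over 6 weeks (Rehabilitation Intervention).
- Three groups, and "Up to thirty older men and women will be enrolled in the intervention component of this study" (Study Overview).
- "Three months after completing the neurorehabilitation program, participants will attend a 3-month follow up assessment session" (Study Overview).

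**Assumptions**
- 10 participants per arm, since no allocation ratio is given.
- Three months taken as 13 weeks.
- Per-session event rate between 0.05 and 0.20, constant over sessions.
- Drop-out in one arm only, with full attendance in the comparator.

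**Step 1: window.** From the first session to the 3-month visit is 6 + 13 = 19 weeks. The logs span 6/19 = 32% of that calendar time, leaving 13/19 = 68% outside them.

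**Step 2: exposure.** Full attendance is 10 × 18 = 180 sessions per arm.
- 3 of 10 stop after session 3: 7 × 18 + 3 × 3 = 135, and 135/180 = 0.75.
- 3 of 10 stop after session 6: 7 × 18 + 3 × 6 = 144, and 144/180 = 0.80.

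**Step 3: effect on the raw count.** Expected count = sessions attended × per-session rate. The ratio of raw counts between arms is therefore E × R, where E is the exposure ratio and R the true per-session rate ratio.

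| True R | Raw ratio, E = 0.75 | Raw ratio, E = 0.80 |
|---|---|---|
| 1.00 | 0.75 | 0.80 |
| 1.25 | 0.94 | 1.00 |
| 1.33 | 1.00 | 1.07 |
| 2.00 | 1.50 | 1.60 |

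At equal risk the less-exposed arm looks safer. At R = 1/E (1.33 or 1.25) the excess disappears. At larger R it is still visible but understated. Under this model, events per session attended estimates R itself in every row.

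At equal risk with E = 0.75, a rate of 0.10 gives 135 × 0.10 = 13.5 expected events against 180 × 0.10 = 18.0. At rates of 0.05 and 0.20 the pairs are 6.75 against 9.0 and 27.0 against 36.0. The ratio is 0.75 throughout.

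**Step 4: how often the less-exposed arm shows the lower count.** This uses two independent Poisson counts with the same per-session rate.

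| Sessions in less-exposed arm | Rate 0.05 | Rate 0.10 | Rate 0.20 |
|---|---|---|---|
| 180 (equal exposure) | 45% | 47% | 48% |
| 144 | 63% | 71% | 80% |
| 126 (70% attendance) | 71% | 81% | 91% |

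Repeated events in the same person would make the counts more variable than Poisson, so these percentages are indicative only.

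**The case against.** The case against giving this much weight is substantial, and most of it limits the point without removing it.

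- **Capture exists.** All adverse events go into the cumulative table, Protection Against Risk says that any event will be recorded, and the DSMB reviews safety and retention. This stands: the gap is in the endpoint definition only. The table is nevertheless not named as the source for Aim 2.
- **Assessment-visit events are not expressly excluded.** A reader might infer that they cannot enter the outcome. The documents do not say so. The same logs are used to judge completion of the post-therapy assessment, so they reach beyond the last session in at least that respect. Inclusion is unclear; exclusion is not established.
- **The denominator is already collected.** Adherence and retention are reported beside the count, so unequal exposure would be visible. This stands too, and it makes the fix nearly free. But no rate is planned, and separate arm totals do not show when events fell relative to drop-out.
- **Calendar time is not risk.** A reader might take 68% of the time as 68% of the safety information. The tDCS Safety paragraph says headache and nausea stop when stimulation ends, section 7 expects exercise discomfort to pass within days, and no stimulation is scheduled after training. An on-treatment outcome is defensible if stated as such.

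**Conclusion.** The point holds as a gap in how the Aim 2 outcome is defined. As written, it is a raw count from the training logs; the three months after training are outside them, the status of assessment-visit events is unclear, and nothing relates the count to exposure.

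The size is conditional. A 25% lower expected count at equal risk requires 10 per arm, 3 of 10 stopping after session 3 in one arm only, full attendance in the other, and events arising in proportion to sessions. With equal attendance the distortion vanishes.

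A reader might also infer that the count is always biased towards no difference, or that it must fall as tolerability worsens. Neither follows. At equal risk, unequal exposure creates a difference, and the count falls only when lost exposure outweighs the higher event rate.

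Priority is modest. This is a planning study of up to 30 participants, and the plan attaches no safety decision rule to the Aim 2 count.

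**What to change.** In section 6, Rehabilitation Intervention, name the cumulative table described under Adverse Event Reporting as the source of the Aim 2 adverse-event outcome, and state the observation window. Report by arm:

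- the number of participants with at least one event;
- on-treatment events per session attended, with the number of sessions shown;
- events after the last session, listed separately from on-treatment events.

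The first two belong together: the number with at least one event limits the influence of one person with many events but still depends on exposure, and the rate addresses exposure.

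Optionally, ask one standard adverse-event question at the existing post-intervention and 3-month visits, so that the later period is covered in the same way in all arms.

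The cost is a few sentences of protocol text and a table built from data already collected, plus one question at two existing visits if that option is taken. The small downside of the question is that more background events unrelated to the intervention will be recorded, which the separate listing keeps apart from the on-treatment comparison.

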#### *Complex Walking Task Intervention*

Two of the three experimental groups will train using complex walking tasks. All of the complex walking tasks that we use have been used previously in our research protocols and/or have been previously reported in the rehabilitation research literature and/or are components of validated clinical instruments. Accordingly, all of the tasks have been demonstrated to be feasible and appropriate for use in our cohort. The following walking tasks will be used: over obstacles, navigating around obstacles, changing speeds, on soft surfaces (exercise mat), in dim lighting, while conversing with the therapist, up/down ramps and climbing/descending stairs.

Progression of training over the course of the intervention will be accomplished by combining these tasks to increase complexity.

#### *Steady State Walking Intervention*

The steady state walking intervention will be conducted similarly to the complex walking intervention, but training will be limited to performance of typical steady state walking.

#### *Transcranial Direct Current Stimulation (tDCS)*

During therapy session, all participants will receive active or sham tDCS, which is a mild form of non-invasive brain stimulation. The electrode placement for the tDCS is designed to engage the frontal lobes bilaterally. tDCS will be applied and operated by research personnel listed in myIRB (with all required training in human subjects research) who have been thoroughly trained in the use and safety of tDCS by the investigative team.

Active tDCS: For each session, a Soterix Direct Current Stimulator will apply up to 30 minutes of 2.0mA direct current through two biocarbon rubber electrodes encased in saline soaked 5cm^2 sponges (10cc of 0.9% saline solution) placed over the frontal cortices at F3 and F4 (based on the “10-20 system” of brain mapping). Current inflow will occur on the right (F4), and outflow on the left (F3). Impedance quality will be  $\leq 10\text{k}\Omega$  to insure proper stimulation of brain tissue.

Sham tDCS: Sham stimulation is performed with the same device and all procedures will be identical except for the duration of stimulation. Participants will receive 30 seconds of 2 mA of direct current stimulation at the beginning of the session. Participants habituate to the sensation of tDCS within 30-60 seconds of stimulation. This procedure provides the same sensation of tDCS without the full duration of stimulation, making it a highly effective sham procedure.

During assessment or rehabilitation sessions, videos and/or photos may be taken during to document the functional abilities of participants, and for possible use in research presentations or education. At the time of consent, participants will choose what their videos/photos can be used for. We will avoid capturing images of the participants face, and will delete any such images that are accidentally captured.

---

#### **Post-Intervention Assessment and 3-Month Follow-Up Assessment**

The procedures will be identical to what is described for the baseline assessment

---

#### **7. Possible Discomforts and Risks:**

As with all physical activity, there is a risk of falling while we test or train walking ability. Falls can lead to injuries ranging from minor to serious. It is also possible that participants could experience musculoskeletal injury such as an ankle sprain. It is possible that the participant may experience fatigue, soreness, and discomfort due to physical activity associated with this study. These are unlikely to be worse than what he/she would experience due to increased physical activity outside of our study. These are normal responses to exercise and most discomfort would generally disappear within a matter of days. In general, walking exercise is strongly recommended for all adults, including elderly adults with medical conditions.

Transcranial direct current stimulation is considered safe but some people do experience some side effects. The most common side effects are itching and tingling or mild discomfort at the area of stimulation, and headache. Other possible but uncommon side effects include dizziness and nausea. Whenever an electrical stimulation is applied to the body, it could possibly cause a

seizure or abnormal heartbeat, but this has never occurred with the transcranial direct current stimulation parameters used in this study. tDCS will be applied and operated by research personnel listed in myIRB (with all required training in human subjects research) who have been thoroughly trained in the use and safety of tDCS by the investigative team.

fNIRS is considered safe. The infrared light used in assessment is not known to cause any harm to alter the brain in any way. The sensors are secured to the participant's head using adhesive tape, which may cause minor skin irritation in some people, or more substantial irritation in people who are sensitive/allergic to adhesives. We will check with participants about any known sensitivities to adhesives.

There is a risk that participants may find cognitive and functional tests challenging or uncomfortable if they have difficulty succeeding with the tasks. Participants may skip any question that they do not wish to respond do.

